7.3 Exclusion Criteria

Subjects must be excluded from participating in this study if they meet any of the following Exclusion Criteria:

- 1) Subject, who, for any reason, is judged by the Investigator to be inappropriate for this study, including a subject who is unable to communicate or cooperate with the Investigator, who has/had a psychiatric illness, disability or social situation that may compromise the safety of the subject during the study or affect the ability of the subject to adhere to study procedures;
- 2) Subject has a medical history of clinically significant (as determined by the Investigator or the Sponsor) cardiac, renal, hepatic/biliary (e.g., sclerosing cholangitis), pulmonary, or other medical conditions or is not generally in good health.

Subjects with the history of immunologic, autoimmune or chronic inflammatory disorders (e.g., uveitis, rheumatoid arthritis, ankylosing spondylitis or spondyloarthritis, psoriasis) other than UC or autoimmune connective tissue diseases (e.g., systemic lupus erythematosus, systemic sclerosis) and are well controlled may be included into the trial after consultancy with medical monitor. Subjects with thyroid disorders, vitiligo, and alopecia are eligible for inclusion.

- 3) Subject's UC had failed to respond to:
 - a) Two or more biologic treatments with different mechanisms of action (e.g., infliximab, vedolizumab and golimumab), or
 - b) Three or more anti-TNF biologics, e.g., infliximab, adalimumab;
- 4) Subject requires prescription treatment for UC, except for the stable, oral treatment of UC as follows:
 - a) Aminosalicylates (5-ASA acid or mesalamine ≤ 4.8 g/day; sulfasalazine ≤ 3 g/day) for at least 14 days prior to the Screening visit; and/or
 - b) Glucocorticoids (≤ 20 mg/day prednisolone or the equivalent, or budesonide ≤ 9 mg/day) for at least 14 days prior to the Screening visit (or for 4 weeks if a course of corticosteroids had started at less than 8 weeks prior to Screening visit); and/or
 - c) Azathioprine up to 3 mg/kg/day or 6-mercaptopurine up to 1.5 mg/kg/day for a total treatment period of at least 12 weeks, including 4 weeks of stable treatment, prior to the Screening visit.
- 5) Subject has received any of the following prior treatments or treatments within the specified time:

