For subjects in all cohorts, a sigmoidoscopy with biopsy will be performed at Week 12 to assess improvement in the mucosa based on a mean change in the mMES from Baseline (Week 0) to Week 12. It is highly recommended that the sigmoidoscopy with biopsy be performed within 7 to 13 days prior to the Week 12 visit.

8.1.4.2 Open-label/Long-term Extension Maintenance Therapy: Week 12 (First Dose) to Week 52

All subjects who qualify and continue double-blind LTE or start open-label maintenance therapy will be administered one KHK4083 or placebo (LTE) or one KHK4083 (OLE) IV infusion at Weeks 12, 16, 20, 24, 28, 32, 36, 40, 44, and 48 for a total of 10 additional treatments followed by an End-of-OLE/LTE Therapy visit at Week 52, and then proceed to the OLE/LTE Therapy Follow-up Period (Week 56 through Week 64). The treatment at Week 12 will be administered at the scheduled visit or within 7 days after Week 12. The OLE dose will be the same as the dose for that cohort during the induction therapy, unless dose-reduction is recommended by the Safety Monitoring Committee and Sponsor (see Section 6.3).

During OLE/LTE Therapy, corticosteroid (glucocorticoid) dosages of prednisolone or its equivalent will be permitted to be tapered (decreasing by up to 2.5 mg/day per week) and other concomitant medications for UC may be tapered. Bolus or “rescue” treatment with systemic corticosteroids or topical corticosteroid enemas or suppositories (in addition to the dose of oral corticosteroids at Screening) is permitted only after Week 12 evaluations are

complete. A sigmoidoscopy with biopsy will be performed at the End-of-OLE/LTE Therapy visit at Week 52 or within 21 days prior to Week 52.

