8.5 Prior and Concurrent Therapy

All medications (including prescription, non-prescription and supplements) for treatment of UC taken within 6 months prior to Screening; any other medication taken 1 month prior to Screening; and any concomitant medications (including tracking probiotic usage) during the study will be collected. For all biologic treatments, the reason for discontinuation should be collected at Screening. Combination medications should be recorded by trade name.

Stable doses of the following concomitant medications are permitted for UC treatment during the study as specified below:

- Aminosalicylates (5-ASA or mesalamine ≤ 4.8 g/day; sulfasalazine ≤ 3 g/day) for at least 14 days prior to the Screening visit; and/or
- Oral glucocorticoids, ≤ 20 mg/day prednisolone or the equivalent, or budesonide ≤ 9 mg/d for at least 14 days prior to the Screening visit (or for 4 weeks if a course of corticosteroids had started at less than 8 weeks prior to Screening visit); and/or
- Azathioprine up to 3 mg/kg/day or 6-mercaptopurine up to 1.5 mg/kg/day for a total treatment period of at least 12 weeks, including 4 weeks of stable treatment, prior to the Screening visit.

Supportive therapy to manage symptoms or AEs is acceptable. Daily, chronic antidiarrheals should not be taken.

One bolus or “rescue” treatment for up to 7 days with each of the following: systemic corticosteroids or topical corticosteroid enemas or suppositories (in addition to the dose of oral corticosteroids at Screening) is permitted only after Week 12 evaluations are complete. Topical anti-inflammatory agents may be permitted only after Week 12 evaluations are complete and application must be withheld for at least 2 weeks prior to the sigmoidoscopy at Week 52/End-of-Treatment visit.

Dose reductions of concurrent medications are permitted for AEs from Baseline through the end of the study as allowed by the protocol. Other dose adjustments of concurrent medications (including corticosteroids and other treatments for UC) are permitted after the Week 12 visit (per Investigator’s judgment), i.e., during OLE/LTE Therapy and the Induction Therapy and OLE/LTE Therapy Follow-up Periods. After the Week 12 visit, corticosteroid (glucocorticoid) dosages of prednisolone or its equivalent may be tapered by approximately 2.5 mg/day per week, at the Investigator’s discretion. Subjects who have recurrence of clinical symptoms may increase their chronic (> 7 days) dose of corticosteroids and other

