10.3 Exploratory Endpoints

Efficacy and PD exploratory endpoints will be included in this study for all subjects with moderately active UC who receive both Induction Therapy and OLE/LTE Maintenance Therapy. The exploratory endpoints for all subjects who receive both Induction Therapy and OLE/LTE Maintenance Therapy are as follows:

- Clinical improvement at Week 52;
Improvement will be based on a reduction (mean change from Baseline [Week 0] to Week 52) in the total Mayo Clinic score (0 to 12).
- Clinical improvement at Weeks 16, 20, 24, 28, 32, 36, 40, 44, 48, and 52 and at OLE/LTE Therapy Follow-up Period visits (Weeks 56, 60, and 64);
Improvement will be based on mean changes from Baseline (Week 0) in the partial (excludes endoscopy subscores) Mayo Clinic score (0 to 10).

- Clinical response at Week 52;
A clinical response is defined as a reduction in the total Mayo Clinic score of at least 3 points and a decrease of at least 30% from Baseline (Week 0) to Week 52, and a reduction in the rectal bleeding subscale of at least 1 point from Baseline (Week 0) to Week 52 or an absolute rectal bleeding score of 0 or 1 at Week 52.
- Clinical remission (i.e., a total Mayo Clinic score of ≤ 2 and no subscores > 1) at Week 52;
- Durable clinical responses and durable clinical remissions at Week 52 (i.e., present at both Week 12 and Week 52), and glucocorticoid-free clinical remission at Week 52;
- Mucosal healing (i.e., an mMES of 0 or 1) at Week 52;
- Improvement in the mucosa according to the following assessments:
 - At least a 1-point improvement in the mMES from Baseline (Week 0) to Week 52;
 - A mean change in the UCEIS score from Baseline (Week 0) to Week 52; and/or
 - At least a 1-point improvement in the modified Baron endoscopic score from Baseline (Week 0) to Week 52.
- Remission (i.e., mMES of 0 or 1, stool frequency subscore of 0 or 1, and rectal bleeding subscore of 0) rates at Week 12 and Week 52;
- Improvement in the HRQL, which will be based on the subject's completed IBDQs;
- Lowered corticosteroid (glucocorticoid) dosages;
- Glucocorticoid-free treatment duration from Week 16 through Week 52, and through the OLE/LTE Therapy Follow-up Period (Week 56 through Week 64);
- PD profile of KHK4083;
- PK-PD relationships.

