 - Glucocorticoid-free clinical remission at Week 52 will be defined in the case that clinical remission is present at Week 52 and no glucocorticoid listed in Section 9.3 is used from Week 16 through Week 52.
- Glucocorticoid dosages:
 - Baseline glucocorticoid dosages (times) will be defined as the total number of administrations of glucocorticoid listed in Section 9.3 that is used during Double-Blind Induction Period (from Day 1 to a day before Week 16). For the subject who receives no glucocorticoid, the dosages will be 0.

	Forms			
	Title	Statistical Analysis Plan Template		
	Code	Version	Effective Date	Page
	FRM_ST03_032	01	23 Apr 2015	32 of 53

- Glucocorticoid dosages (times) at Week 16 through Week 52 will be defined as the total number of administrations of glucocorticoid listed in Section 9.3 that is used during OLE/LTE Therapy Period (from Week 16 to Week 52). For the subject who receive no glucocorticoid, the dosages will be 0.
- Glucocorticoid dosages (times) at Week 16 through LTE Therapy Follow-up Period will be defined as the total number of administrations of glucocorticoid listed in Section 9.3 that is used during LTE Therapy Period and LTE Therapy Follow-up Period (from Week 16 to Follow-up 3). For the subject who receives no glucocorticoid, the dosages will be 0.
- Glucocorticoid dosages (times) at Week 16 through OLE Therapy Follow-up Period will be defined as the total number of administrations of glucocorticoid listed in Section 9.3 that is used during OLE Therapy Period and OLE Therapy Follow-up Period (from Week 16 to Follow-up 3). For the subject who receives no glucocorticoid, the dosages will be 0.
- If there is glucocorticoid that the number of administrations is unknown, it will be assumed that the glucocorticoid was used at a frequency of an administration per day.
- For the subjects who do not move to OLE/LTE Therapy Period, “Glucocorticoid dosages (times) at Week 16 through Week 52” and “Glucocorticoid dosages (times) at Week 16 through OLE/LTE Therapy Follow-up Period” will not be defined.
- Change from baseline in corticosteroid (glucocorticoid) dosages will be defined as follows:
 - Change from baseline in corticosteroid (glucocorticoid) dosages at Week 16 through Week 52 = Glucocorticoid dosages at Week 16 through Week 52 - Baseline glucocorticoid dosages

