 - Change from baseline in corticosteroid (glucocorticoid) dosages at Week 16 through LTE Therapy Follow-up Period = Glucocorticoid dosages at Week 16 through LTE Therapy Follow-up Period - Baseline glucocorticoid dosages
 - Change from baseline in corticosteroid (glucocorticoid) dosages at Week 16 through OLE Therapy Follow-up Period = Glucocorticoid dosages at Week 16 through OLE Therapy Follow-up Period - Baseline glucocorticoid dosages
- Duration of glucocorticoid-free treatment will be defined as the duration that no glucocorticoid listed in Section 9.3 is used from Week 16 through Follow-up 3.
 - Duration of glucocorticoid-free treatment (days) = Date of first glucocorticoid after Week 16 visit - Date of Week 16 visit
 - If the subject received glucocorticoid on the date of Week 16 visit, the duration of glucocorticoid-free treatment for the subject is 0.

A comparison between treatments (each KHK4083 dose level versus placebo) will be performed using an ANCOVA model with changes from Baseline in UCEIS, total Mayo Clinic score and partial Mayo Clinic score at Week 52 during Double-Blind Therapy Period as dependent variables, treatment as fixed effect and baseline value as covariate. The number of subjects and the number of subjects considered in the model will be provided by treatment. The adjusted means for treatments (least squares means) and the relative 95% CIs will be presented. The difference between the adjusted means for each treatment groups from placebo (Difference in Least Squares Mean from Placebo) will be calculated with the relative 95% CI and p-value. If ANCOVA cannot be applied

	Forms			
	Title	Statistical Analysis Plan Template		
	Code	Version	Effective Date	Page
	FRM_ST03_032	01	23 Apr 2015	33 of 53

due to the issue that the parameters cannot be estimated appropriately, these analyses using ANCOVA for Week 52 will not be applied.

Means with SDs for the efficacy variables (mMES, UCEIS, total Mayo score and partial Mayo score) at all visits will be performed graphically by each treatment (e.g. Placebo, 1.0 mg/kg, 3.0 mg/kg, or 10 mg/kg) and by Double-Blind Therapy Period and OLE Therapy Period. For partial Mayo score, Means with SDs as all visits will be performed graphically by “Double-Blind Therapy Period and Double-Blind Therapy Follow-up Period” and “OLE Therapy Period and OLE Therapy Follow-up Period”. Mean changes from Baseline will also be performed in the same manner.

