The derived variables will be identified in the listings with a flag (*).

Tabular display of data for prior / concomitant medications, and all tabular displays of adverse event data should be presented by the body system, drug class, or SOC with the highest occurrence in the active treatment group (KHK4083 combined group) in decreasing order. Within the body system, drug class and SOC, medical history (by Preferred Term), drugs (by ATC1 code), and adverse events (by Preferred Term) should be displayed in decreasing order. If incidence for more than 1 term is identical, they should then be sorted alphabetically.

In general, dates will be presented on listings in the format ddmmyyyy (date9.) and time in the format hh:mm (time5.). In case of partial dates or times, missing information will be replaced by dashes. Numeric variables will be listed generally with the same number of decimal places as in the actual data.

The following rules on decimal places will be considered in the listings for the derived variables (in the analyses approximations will not be performed):

- Age (years), duration of treatment (days): 0 decimal place;
- Change from baseline: same as the variable considered.

The following rules on decimal places will be considered for the results of the analyses (if the analyses are performed on derived variables, the level of precision of the actual data is derived from the previous list):

- Min, max: same as actual data;
- Mean and its confidence limits (unadjusted and adjusted), adjusted difference between means and its confidence limits, SD, median: actual data + 1 decimal;
- Percentage: 1 decimal place.

	Forms			
	Title	Statistical Analysis Plan Template		
	Code	Version	Effective Date	Page
	FRM_ST03_032	01	23 Apr 2015	39 of 53

9.3 **Glucocorticoid**

Among concomitant medications which started to be administered from Day 1, those corresponding to the list below will be defined as glucocorticoid and considered in Tables and Listings relative to glucocorticoid.

- Medications that ATC code is “H02AB” (that is assigned to “Glucocorticoids”).

	Forms			
	Title	Statistical Analysis Plan Template		
	Code	Version	Effective Date	Page
	FRM_ST03_032	01	23 Apr 2015	40 of 53

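### The SAP's glucocorticoid-free endpoints misclassify subjects: read literally they ignore pre-study steroid, if it is meant to count they fail on-schedule taperers from the highest permitted doses, and the duration formula has no value for subjects who take none

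*SAP*

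**What the plan says.** Protocol 10.3 lists "glucocorticoid-free clinical remission at Week 52" as an exploratory endpoint and attaches no earlier steroid-free period to it. Steroid-free treatment duration from Week 16 is a separate item in that list. Protocol 5 also has a separate objective on the percentage of subjects free of glucocorticoid from Week 16 through Week 52.

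SAP 7.3 defines the remission endpoint as met when "clinical remission is present at Week 52 and no glucocorticoid listed in Section 9.3 is used from Week 16 through Week 52". It calculates steroid-free duration as "Date of first glucocorticoid after Week 16 visit - Date of Week 16 visit", and sets it to 0 if a glucocorticoid is taken on the date of the Week 16 visit.

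SAP 9.3 decides what counts: "Among concomitant medications which started to be administered from Day 1, those corresponding to the list below will be defined as glucocorticoid". The list is then ATC code H02AB.

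Protocol 8.5 permits stable oral background steroid at "≤ 20 mg/day prednisolone or the equivalent, or budesonide ≤ 9 mg/d for at least 14 days prior to the Screening visit", with a 4-week requirement for more recently started courses. On tapering, protocol 8.1.4.2 says that during the extension the dose "will be permitted to be tapered (decreasing by up to 2.5 mg/day per week", and 8.5 says that after the Week 12 visit it "may be tapered by approximately 2.5 mg/day per week". Before that visit, 8.5 allows reductions of concurrent medication for adverse events only.

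**The concern.** Both endpoints depend on which steroid use is counted and from when, and the documents do not fit together on either question. The SAP's list of counted drugs appears to leave out the steroid that subjects bring into the trial. If that steroid is counted after all, the steroid-free period begins before a subject on a high permitted dose can complete a taper that itself begins only after Week 12.

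The objective is to learn whether KHK4083 induces remission without steroid. Subjects who enter on steroid are the ones in whom that question is informative. If they are classified by entry dose, or by how their medication was recorded, the rate says little about the drug. With about 60 subjects spread over placebo and up to three dose levels, a few misclassifications can visibly change a group's percentage.

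**Working it through.** The plan states no rate, count or power for these endpoints, so there is no figure of its own to reproduce. The check sets the definitions beside the taper rule.

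**Inputs.** Highest background dose 20 mg/day (protocol 7.3 criterion 4b and 8.5). Taper 2.5 mg/day per week after Week 12 (8.1.4.2, 8.5). Steroid-free period from Week 16 (SAP 7.3). Visit windows: Week 12 ± 4 days (Table 9-1), Week 16 ± 7 days (Table 9-2).

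**Reading A: SAP 9.3 taken literally.** Both routes to permitted background steroid require it to have been in use before Screening, so it started before Day 1. SAP 5.5 defines concomitant medications as those started at any time and taken during the study; SAP 9.3 then narrows these to medications started from Day 1. A continuing background steroid is therefore not counted at any dose. A subject in clinical remission at Week 52 and still on 20 mg/day meets the definition.

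**Reading B: background steroid counts.** Steps needed = dose / 2.5, rounded up. Steroid-free week = 12 + steps − 1 if the first cut is at Week 12, or 12 + steps if it comes a week later. Steroid-free weeks before Week 52 = 52 − that week.

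| Dose at Week 12 (mg/day) | Steps | Off steroid at week | Steroid-free weeks to Week 52 |
|---|---|---|---|
| 10 | 4 | 15 or 16 | 37 or 36 |
| 12.5 | 5 | 16 or 17 | 36 or 35 |
| 15 | 6 | 17 or 18 | 35 or 34 |
| 17.5 | 7 | 18 or 19 | 34 or 33 |
| 20 | 8 | 19 or 20 | 33 or 32 |

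The largest dose that can be cleared by the Week 16 visit depends on the days between the two visits:

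- Nominal, 28 days: 4 × 2.5 = 10, or 5 × 2.5 = 12.5 mg/day.
- Longest, 28 + 4 + 7 = 39 days: 5 × 2.5 = 12.5, or 6 × 2.5 = 15 mg/day.
- Shortest, 28 − 4 − 7 = 17 days: 2 × 2.5 = 5, or 3 × 2.5 = 7.5 mg/day.

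Under this reading a subject tapering from 20 mg/day also scores duration 0. If off steroid from Week 20 to Week 64, that subject has (64 − 20) × 7 = 308 steroid-free days and scores the same as one who never tapers.

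**Which reading was meant?** SAP 7.3 defines baseline glucocorticoid dosages from Section 9.3 drugs used between Day 1 and the day before Week 16, and then a change from that baseline. Protocol 8.5.1 bars steroid increases and rescue during induction, so under Reading A that baseline would be largely empty. This points to Reading B, but the wording of 9.3 points to A. The documents also do not say whether a taper step is entered as a new medication record. If it is, Reading A could fail the subject who tapers and pass the one who does not.

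**Duration under either reading.** The formula needs the date of a first glucocorticoid after Week 16. A subject who takes none has no such date and so no value, and protocol 12.6 leaves missing values as missing. At the other extreme, a permitted systemic rescue course of up to 7 days (8.5) that includes the Week 16 visit date gives 0, although it uses at most 7 of the (64 − 16) × 7 = 336 days to Week 64.

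**The case against.** The strongest reply is that Week 16 is the protocol's own date. It appears in the objective on the percentage of subjects free of glucocorticoid and in the duration endpoint, and requiring sustained freedom from steroid is a legitimate, stricter claim. That stands as a reason to keep a Week 16 to 52 result. It does not justify using that window as the only definition of an endpoint that the protocol lists separately as remission at Week 52.

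On duration, the sentence introducing the formula runs the period through Follow-up 3, so a programmer could use that visit as the end date for subjects who take no steroid. That is a sensible guess, but the formula does not say it and gives no rule for subjects lost before Follow-up 3.

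The consequences are also limited. Protocol 12.3.5 makes all analyses descriptive or exploratory. These variables are not among the Week 12 tables in SAP 9.4.1 that support the proof-of-concept decision, nor in the ANCOVA or MMRM comparisons. Clinical remission at Week 52 is summarised regardless of steroid use. All of this stands: it bounds the importance of the point without removing the misclassification.

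**Conclusion.** The point holds, for exploratory endpoints only. SAP 7.3, SAP 9.3 and protocol 8.1.4.2 and 8.5 do not give a usable classification under either reading. Under A, continuing pre-study steroid of up to 20 mg/day is invisible. Under B, on-schedule taperers from above about 10 to 12.5 mg/day (12.5 to 15 mg/day at the longest visit windows) will generally be failed. The missing duration value for subjects who take no steroid after Week 16 holds under both.

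A reader might infer that subjects on the higher doses cannot qualify at all, or that hundreds of steroid-free days are necessarily recorded as 0. The documents do not support that. Both statements depend on Reading B, and the literal text of 9.3 gives the opposite result. Even under B, adverse-event reductions are allowed from Baseline, 8.5 says only approximately 2.5 mg/day, and the visit windows move the cut-off. The 32 to 33 weeks apply only to the 20 mg/day maximum.

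The number of subjects on steroid, and their doses, are not given, so the effect on any group's rate cannot be sized.

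**What to change.** Change the SAP only. The taper rule is a clinical matter and is left as it is, though 8.1.4.2 and 8.5 describe the rate differently and should be reconciled.

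1. **SAP 9.3:** count any listed glucocorticoid in use on or after Day 1, including one started earlier and still ongoing.
2. **SAP 7.3, remission:** require clinical remission at Week 52 and no counted glucocorticoid in a fixed window that ends at Week 52 and begins after the longest on-schedule taper can finish. The arithmetic puts that finish at about Week 20. A start at Week 40 is one illustration that leaves room for tapers begun late; it is not a figure from the documents. Report the Week 16 to 52 version as supportive, because the protocol has a separate objective for that period.
3. **SAP 7.3, duration:** use total days without counted glucocorticoid from the Week 16 visit to Follow-up 3 or last contact, crediting subjects who use none with their full observed time. Show observed days alongside, since the total depends on length of follow-up.

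The cost is SAP wording and derivation code. SAP 5.5 already relies on medication start and stop dates, so no new data are needed. The downside is that a shorter steroid-free window is a less strict claim, which the supportive analysis offsets.
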